5.2.4 Data scope post-NOAF analysis

Date of NOAF requiring treatment with high dose oral anticoagulation

Date NOAF is defined as the date where treatment with high dose oral anticoagulation for NOAF is started. Information is derived from study drug exposure form for Rivaroxaban or VKA in combination with ECG evidence of NOAF.

Start of follow-up in post-NOAF analysis

Day 1 in post NOAF analysis is the date of NOAF as defined above.

Censoring of follow-up in post-NOAF analysis

Censoring of follow-up for subjects is on the efficacy cut-off date, or date of last known visit, whichever comes first.

Only subjects that start OAC treatment as described in the protocol section 7.1.1.1 and 7.1.2.1 are included from the post-NOAF analysis.

6. Statistical Methodology

6.1 Population characteristics

6.1.1 Disposition

The following will be tabulated overall and/or by treatment group:

- Study sample size (FAS)
- Study sample size by region, country and site (FAS)

Region is defined as follows:

North America: Canada, USA

Eastern Europe: Czech Republic, Poland

Western Europe: Austria, Belgium, Denmark, France, Germany, Italy, Netherlands, Norway, Spain, Sweden, Switzerland, UK

- Number of subjects by primary reason for screening failure (overall only, subjects screened)
- Number of subjects with permanent discontinuation of randomized treatment strategy (FAS)
- Number of subjects and primary reason for discontinuation from the study (FAS)

6.1.2 Demographics

The following demographic and baseline characteristics will be summarized by treatment group in FAS. Summary statistics will be presented for metric variables and frequency tables will be presented for categorical variables.

- Sex (% male)
- Age (continuous, year)
- Age (categorical <median, \geq median, \leq 75 year, $>$ 75 year, \leq 85 year, $>$ 85 year)
- Weight (continuous, kg)
- BMI (continuous, kg/m²)
- Ethnicity (categorical as specified in eCRF)
- Race (categorical as specified in eCRF)
- Current/recent smoker (<1 year) (% yes)
- Diabetes mellitus (% yes,)
- eGFR at screening (<30 ml/min/1.73m², \geq 30 to \leq 50 ml/min/1.73m², $>$ 50 to \leq 80 ml/min/1.73m², $>$ 80 ml/min/1.73m²)

Other baseline characteristics may be added.

6.1.3 Medical history

Medical history data will be evaluated by treatment group in FAS. Frequency tables, showing the number if subjects with medical history findings that started before signing of the informed consent and that are considered relevant to the study.

Medical history findings, of the pre-specified CRF items as listed, will be coded by Medical Dictionary for Regulatory Activities (MedDRA) codes. Medical history will be presented for each MedDRA Primary System Organ Class (SOC) and Preferred Term (PT) by treatment group and overall based on FAS. Medical History of the category “Other” will be presented if the frequency of PT is 5% or higher. In addition, medical history will be presented by the pre-specified terms as listed in the CRF:

- Arterial hypertension (% yes)
- Congestive heart failure (left ventricular dysfunction) (% yes)
- Myocardial infarction (% yes)
- Percutaneous Coronary Intervention (% yes)
- Coronary Artery Bypass Graft (% yes)
- Stroke (% yes)
- Transient Ischemic Attack (% yes)
- Peripheral artery disease (% yes)
- Non-CNS systemic embolism (% yes)
- Venous thromboembolism (% yes)
- COPD (% yes)

6.1.4 TAVR details

The following TAVR details will be summarized by treatment group in FAS. Summary statistics will be presented for metric variables and frequency tables will be presented for categorical variables as specified in [4.1](#)

- TAVR due to subjects frailty (% yes)
- EuroScore II (final) (continuous)
- STS score (final) (continuous)
- Brand name of aortic valve (categorical as specified in eCRF)
- Size of aortic valve (continuous)
- Valve in valve procedure (% yes)

6.1.5 Randomization timing

Timing of randomization (number of days post TAVR) is summarized by treatment group in FAS.

6.1.6 Protocol deviations

Protocol deviations will be summarized by treatment group in FAS. Frequency tables will be presented by type of deviation.

6.1.7 Prior and concomitant medications

Frequency tables by ATC code will be provided for prior medications prior to randomization and for concomitant medication post-randomization. The summaries will be by treatment group and overall based on FAS.

6.1.8 Extent of exposure and Compliance

All summaries related to intake of study medication will be by treatment group based on FAS.

The treatment duration (date of last study medication – date of start first study medication +1) will be summarized descriptively.

The time on study medication (treatment duration excluding days off study medication) will be calculated and summarized descriptively.

6.2 Efficacy

The primary efficacy endpoint is death or first adjudicated thromboembolic event (DTE), defined as the adjudicated composite of

- All-cause death
- Any stroke
- Myocardial infarction (MI)
- Symptomatic valve thrombosis
- Pulmonary embolism (PE)
- Deep vein thrombosis (DVT)
- Non-central nervous system (CNS) systemic embolism

The endpoint definitions are located in sections 16.1 and 16.2 of the protocol.

The secondary efficacy endpoints, analyzed hierarchically, are

- The adjudicated composite of cardiovascular death (including unknown of unexplained death), any stroke, myocardial infarction, symptomatic valve thrombosis, pulmonary embolism, deep vein thrombosis, or non-CNS systemic embolism
- The net-clinical-benefit defined as the adjudicated composite of all-cause death, any stroke, myocardial infarction, symptomatic valve thrombosis, pulmonary embolism, deep vein thrombosis, non-CNS systemic embolism (efficacy); life-threatening, disabling and major bleeds (safety).

6.2.1 Analysis of the efficacy endpoints

The analysis of the primary efficacy endpoint (DTE) and the secondary efficacy endpoints are performed on the FAS under the ITT scope. See chapter 5 for details.

In order to preserve the type I error rate for efficacy testing, there is a hierarchy in testing for the efficacy endpoints, first a non-inferiority testing of the primary efficacy endpoint (DTE) is performed. If non-inferiority can be claimed for the rivaroxaban-based strategy a superiority testing of the primary efficacy endpoint (DTE) is performed. If superiority can be declared for the rivaroxaban-based strategy the secondary efficacy and net-benefit variables are tested sequentially in a hierarchical order, first the composite of cardiovascular death, any stroke, myocardial infarction, symptomatic valve thrombosis, pulmonary embolism, deep vein thrombosis, or non-CNS systemic embolism, second the net-clinical-benefit defined as the adjudicated composite of all-cause death, any stroke, myocardial infarction, symptomatic valve thrombosis, pulmonary embolism, deep vein thrombosis, non-CNS systemic embolism (efficacy); life-threatening, disabling and major bleeds (safety). These are tested at a one-sided significance level of 2.5%

If there is strong evidence of non-proportionality, the estimation of time-dependent hazard ratios will be considered.

The analysis of the primary efficacy endpoint is visualized in [flowchart 1](#) in appendix I, the analysis of the secondary efficacy endpoints are visualized in [flowchart 2](#) in appendix I.

Details of the tests in the following sections.

6.2.1.1 Testing for non-inferiority

Testing for superiority of the rivaroxaban-based strategy for the primary efficacy outcome is preceded by testing for non-inferiority, in the OT data scope, tested with the non-inferiority log rank test⁸.

Using an non-inferiority log rank test the following (inferiority) null hypothesis (H_0) is tested at a one-sided significance level of 2.5%:

$H_0: \widehat{HR}(t) \geq 1.20$ for all time points $t \geq 0$, (i.e. “the hazard for the primary efficacy endpoint in the rivaroxaban-based treatment group is more than 20% larger than that in the antiplatelet-based control group regarding”)

The one-sided alternative hypothesis (H_1) is:

Statistical Analysis Plan

Study No.: BAY59-7939-17938

Page: 17 of 31

$H_1: \widehat{HR}(t) < 1.20$ for all time points $t \geq 0$, (i.e. “the hazard in the rivaroxaban-based treatment group for the primary efficacy endpoint is such that the \widehat{HR} is below 1.20”)

The following decision rule to test the null hypothesis of inferiority is applied:

With the estimated drift parameter $\hat{q} = Z/V$ where Z is the LR statistic with its Variance V (note that $V \approx \text{events}/4$) and $\widehat{HR} = \exp(-\hat{q})$, the upper 97.5% limit of the confidence interval for \widehat{HR} is calculated as

$UL_{0.975}(\widehat{HR}) = \exp\left(-\left(\hat{q} - \frac{1.96}{\sqrt{V}}\right)\right)$ and will be compared with the NIM of 1.2. The null hypothesis $H_0: HR \geq 1.2$ will be rejected if $UL_{0.975}(\widehat{HR}) < 1.2$

If the null-hypothesis of inferiority (H_0) is rejected and non-inferiority of the rivaroxaban-based strategy (relative to the antiplatelet-based strategy) with regard to the primary efficacy endpoint can be claimed, proceed to section [6.2.1.2](#).

The following SAS code can be used to obtain the LR statistic:

```
ods output LogRankHomCov=work.LRHC HomStats=work.HomStats ;
proc lifetest data=work.infile alpha=0.025 method=km notable ;
time d2fDTE * DTE(0) ;
strata treat /test=(logrank) ;
run;

*from ODS datasets to needed variables, and calculations;
data work.logrank (drop=treat) ;
merge work.lrhc (where=(treat='0') keep=treat _0 rename=(_0=V)) 
      work.homstats (where=(treat='0') rename=(LogRank=Z) keep=LogRank
      treat) ;

q=Z/V;
HR=exp(-q);
UL=exp(-(q-(1.96/sqrt(V))));;
label
  Z="LR statistic"
  V="Variance of LR statistic"
  q="q"
  HR="HR"
  UL="Upper limit 0.975"
;
%put "on purpose no by statement for merge, 1 record per input dataset";
run;
/*
where
work.infile = name of source dataset
treat      = randomization code
DTE        = death and thromboembolic event
d2fDTE    = days to first DTE (since randomization)
*/

```

6.2.1.2 Testing for superiority

If, for the primary efficacy endpoint (DTE), non-inferiority of the rivaroxaban-based strategy can be claimed, superiority of the rivaroxaban-based strategy for the primary efficacy endpoint (DTE) is tested with the following hypothesis (H_0) at the significance level of 2.5%

$H_0: S_{RIV}(t) = S_{APT}(t)$ for all time points $t \geq 0$, (i.e. “there is no difference between the rivaroxaban-based treatment group and the antiplatelet-based control group regarding the primary efficacy endpoint at all time points”)

The one-sided alternative hypothesis (H_1) is:

$H_1: S_{RIV}(t) > S_{APT}(t)$ for at least one time point $t \geq 0$, and $S_{RIV}(t) \geq S_{APT}(t)$ for all time points ≥ 0 (i.e. “there is difference between the two groups in favor of the rivaroxaban-based treatment group for the primary efficacy endpoint at all time points”)

where S_{RIV} denotes the event-free survival function of the rivaroxaban-based treatment group and S_{APT} denotes the event-free survival function of the antiplatelet-based treatment group.

The following decision rule to test the null hypothesis is applied:

According to the size of this study, it is justified to assume under H_0 a sufficiently close approximation of the one-sided log-rank test to the normal distribution. If the z value from the one-sided log-rank test (for the difference $S_{RIV}(t) - S_{APT}(t)$) is larger than the critical quantile from the normal distribution ($z_{0.975} = 1.96$), the null hypothesis is rejected in favor of the alternative hypothesis.

Kaplan-Meier curves, one-sided log rank p-value, number of patients with event and incidence rate are provided to evaluate the timing of event occurrence in the different treatment groups and the consistency of the respective treatment effects for all time points.

The following SAS code may be used:

```
proc lifetest data=work.infile  notable;
  time d2fDTE*DTE(0);
  strata treat /test=(logrank);
run;
/*
where
work.infile = name of source dataset
treat       = randomization code
DTE         = death and thromboembolic event
d2fDTE     = days to first DTE (since randomization)
*/

```

If, for the primary efficacy endpoint (DTE), non-inferiority of the rivaroxaban-based strategy can be claimed and the assumption of proportional hazards is plausible (see section 6.2.1.3), Hazard ratio and corresponding two-sided 95% confidence intervals are estimated. This is based on a Cox proportional hazards model, and will be reported descriptively. The parameter estimate β ($=\ln(HR)$), its standard error, p-value, and 95% Confidence Limits are calculated according to the maximum partial likelihood method (ML), with Breslow's approximation for ties (phreg).

The following SAS code may be used:

```
proc phreg data=work.infile ;
  model d2fDTE*DTE(0)=treat /risklimits ;
run;
/*
where
work.infile = name of source dataset
treat       = randomization code
DTE         = death and thromboembolic event
d2fDTE     = days to first DTE (since randomization)
*/

```

If superiority of DTE can be declared for the rivaroxaban-based strategy the secondary efficacy and net-benefit variables are tested for superiority sequentially in a hierarchical order, first the composite of cardiovascular death, any stroke, myocardial infarction, symptomatic valve thrombosis, pulmonary embolism, deep vein thrombosis, or non-CNS systemic embolism, second the net-clinical-benefit defined as the adjudicated composite of all-cause death, any stroke, myocardial infarction, symptomatic valve thrombosis, pulmonary embolism, deep vein thrombosis, non-CNS systemic embolism (efficacy); life-threatening, disabling and major bleeds (safety).

The superiority analysis are carried out under the ITT data scope.

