10.3.5.1. Testing for superiority

This section was modified with Amendment 3. For details, see Section 15.2.

In order to evaluate whether the rivaroxaban-based strategy is superior to the antiplatelet-based strategy in prolonging the time to primary efficacy outcome event in patients with post-TAVR patients, the following null hypothesis (H_0) is tested at the significance level of 2.5%:

$H_0: S_{RIV}(t) = S_{APT}(t)$ for all time points $t \geq 0$, (i.e. “there is no difference between the rivaroxaban-based treatment group and the antiplatelet-based control group regarding the primary efficacy outcome for all time points”)

The one-sided alternative hypothesis is:

$H_1: S_{RIV}(t) > S_{APT}(t)$ for at least one time point $t \geq 0$, and $S_{RIV}(t) \geq S_{APT}(t)$ for all time points $t \geq 0$, (i.e. “there is a difference between the two groups in favor of the rivaroxaban-based treatment group regarding the primary efficacy outcome for at least one time point”)

where S_{RIV} denotes the event-free survival function of the rivaroxaban-based treatment group and S_{APT} denotes the event-free survival function of the antiplatelet-based treatment group.

The following decision rule to test the null hypothesis is applied:

According to the size of this study, it is justified to assume under H_0 a sufficiently close approximation of the one-sided log-rank test to the normal distribution. If the z-value from the one-sided log-rank test (for the difference $S_{RIV}(t) - S_{APT}(t)$) is larger than the critical quantile from the normal distribution ($z_{0.975} = 1.96$), the null hypothesis is rejected in favor of the alternative hypothesis.

Kaplan-Meier estimates of cumulative risk and cumulative hazard functions are provided to evaluate the timing of event occurrence in the different treatment groups and the consistency of the respective treatment effects for all time points.

Hazard ratio and corresponding two-sided 95% confidence intervals are estimated based on a Cox proportional hazards models. The parameter estimate β ($=\ln(HR)$), its standard error, p-value, and 95% Confidence Limits are calculated according to the maximum partial likelihood method, with Breslow's approximation for ties (phreg).

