The plausibility of proportional hazards assumption will be assessed by visually comparing the plot of the log of cumulative hazard between treatments and by additionally adding a treatment by logarithm-transformed time interaction into the Cox model. If there is strong evidence of non-proportionality, the estimation of time-dependent hazard ratios will be considered.

All of the above analyses are carried out under the ITT data scope (i.e. all events are counted irrespective of the actual treatment at the time of the event).

Further details will be specified in SAP.

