10.3.5.2. Testing for non-inferiority

This section was modified with Amendment 3. For details, see Section 15.2.

Using a log rank test adapted to non-inferiority testing the following (inferiority) null hypothesis (H_0) is tested at a one-sided significance level of 2.5%:

H_0 : $HR(t) \geq 1.2$ for all time points $t \geq 0$, (i.e. “the hazard for the primary efficacy endpoint in the rivaroxaban-based treatment group is more than 20% larger than that in the antiplatelet-based control group regarding”)

The one-sided alternative hypothesis (H_1) is:

H_1 : $HR(t) < 1.2$ for all time points $t \geq 0$, (i.e. “the hazard in the rivaroxaban-based treatment group for the primary efficacy endpoint is such that the HR is below 1.20”)

The following decision rule to test the null hypothesis of inferiority is applied:

If the upper boundary of 95% confidence interval (CI) for HR falls below 1.20, the null-hypothesis of inferiority (H_0) is rejected and non-inferiority of the rivaroxaban-based strategy (relative to the antiplatelet-based strategy) with regard to the primary efficacy endpoint can be claimed.

Hazard ratio and corresponding two-sided 95% confidence intervals are estimated based on a Cox proportional hazards model.

In order to preserve the type I error rate for efficacy testing, the two tests for the primary efficacy endpoint are technically placed in a hierarchical order, (1) testing for non-inferiority as described in this section followed by (2) testing for superiority as described in the previous section.

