10.4. Determination of sample size

This section was modified with Amendment 3. For details, see Section 15.2.

The sample size determination for the study was driven by requirements for testing superiority of the rivaroxaban-based strategy over the antiplatelet-based strategy as described above.

The expected 540 days event rate of the primary efficacy endpoint is 33.0% (5-7, 10). The target Relative Risk at 540 days is 0.80, i.e. a reduction of the 540 days event rate from 33.0% under antiplatelet-based regimen to 26.4% under the rivaroxaban-based regimen. Under the assumption of an exponential distribution, the hazard ratio equals 0.7654.

Under the above assumptions, with 360 days accrual period, and an 540 days median follow-up (minimum 360 days and maximum 720 days), randomization of 2 x 740 analyzable subjects is expected to yield 440 primary events (196 in the rivaroxaban-based treatment group and 244 in the antiplatelet-based control group). This provides 80% power at a 5% significance level, without interim analyses for efficacy.

The power calculation was based on a test using the Cox proportional hazards model and was performed with PASS version 12.0.6, with the module for two survival curves using Cox's proportional hazards model.

A sample size of sample size of 2 x 760 subjects allows for an attrition rate of 2.63%. The study is event driven and the number of randomized subjects is estimated to be required to collect 440 primary efficacy events. The study is planned to run until this number of events has been reached or to stop earlier if the event rate is unexpectedly low.

With this sample size, the study has > 90% power to show non-inferiority with a non-inferiority margin of 1.20 if the underlying hazard ratio ≤ 0.90 at a one-sided significance level of 2.5%. The non-inferiority margin of 1.20 was selected based on clinical appropriateness.

The final sample size will depend on multiple factors including the rate of accrual of the primary endpoint events. The Steering Committee of the trial will monitor the aggregate (blinded) event rate and may increase the sample size or duration of follow-up to achieve the planned target number of events in consultation with the sponsor.

Non-inferiority margin

The non-inferiority margin of 1.20 for the HR for the efficacy comparison as described in Section 10.3.5.2 was selected based on both clinical appropriateness and relevant studies in the area of TAVR.

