6.2.1.3 Assessment plausibility of the proportional hazards assumption

If the hypothesis of non-inferiority is accepted the plausibility of the proportional hazards assumption will be assessed by visually comparing the plot of the log of cumulative hazard , in the ITT data scope, between treatments. The following SAS code may be used:

```
proc phreg data=work.infile (where=(treat=1));
model d2fDTE*DTE(0)=treat;
baseline out=work.ch_t1 cumhaz=ch;
run;
proc phreg data=work.infile (where=(treat=0));
model d2fDTE*DTE(0)=treat;
baseline out=work.ch_t0 cumhaz=ch;
run;
data work.log_ch;
set work.ch_t1
      work.ch_t0;
if ch ne 0 then log_ch=log(ch);
run;

proc sgrender data=work.log_ch template=comp_log_CH;
dynamic xvar="d2fDTE" yvar="log_ch" groupvar="treat";
run;

/*
where

```

```
work.infile = name of source dataset
treat       = randomization code
DTE         = death and thromboembolic event
d2fDTE     = days to first DTE (since randomization)
comp_log_ch = proc template for a log of cumulativehazards plot
*/

```

By additionally adding a time-varying covariate, an interaction between the predictor and the time the plausibility of proportional hazards is assessed, the following SAS code may be used:

```
proc phreg data= work.infile;
model d2fDTE * DTE (0)=treat treat_time;
treat_time = treat*log(d2fDTE);
proportionality_test: test treat_time;
run;
/*
where
work.infile = name of source dataset
treat       = randomization code
DTE         = death and thromboembolic event
d2fDTE     = days to first DTE (since randomization)
*/

```

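### The SAP makes the ITT hazard ratio, its confidence interval and the proportional-hazards check for DTE conditional on on-treatment non-inferiority; the protocol does not

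*SAP*

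**What the plan says.** SAP 6.2.1.1 tests non-inferiority of DTE "in the OT data scope, tested with the non-inferiority log rank test", against a margin of 1.20. SAP 6.2.1.2 then conditions the superiority test on that result. Further down, it states a condition again for the estimate: the Cox hazard ratio and two-sided 95% interval are produced if "non-inferiority of the rivaroxaban-based strategy can be claimed and the assumption of proportional hazards is plausible". The same paragraph calls this estimate descriptive, and the section closes by placing its analyses in the ITT scope. SAP 6.2.1.3 opens: "If the hypothesis of non-inferiority is accepted the plausibility of the proportional hazards assumption will be assessed".

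Protocol 10.3.5.1 plans the same outputs without either condition: "Hazard ratio and corresponding two-sided 95% confidence intervals are estimated based on a Cox proportional hazards models". It then plans the proportional-hazards assessment, says time-dependent hazard ratios will be considered if non-proportionality is strong, and adds: "All of the above analyses are carried out under the ITT data scope". The ordering rule is in Protocol 10.3.5.2, where it exists to preserve the type I error rate: "the two tests for the primary efficacy endpoint are technically placed in a hierarchical order". The readable text of SAP section 7 records no changes to the planned analysis.

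**The concern.** A hierarchy protects a hypothesis test. A descriptive estimate uses no alpha and does not need that protection. Under the SAP wording, whether the plan specifies the main ITT effect size depends on a favourable result in a different data scope, so availability of the estimate follows the direction of the result.

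The SAP is also uneven within itself:

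- Section 6.2.1 says time-dependent hazard ratios will be considered under strong non-proportionality, with no non-inferiority condition. The check that would supply that evidence for DTE does carry the condition.
- Section 6.4.1.1 requires only plausible proportional hazards for the bleeding hazard ratio.
- Section 6.6.1 states no non-inferiority condition for the ITT subgroup hazard ratios.

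After a failed non-inferiority test, the SAP would therefore specify a bleeding hazard ratio and a subgroup forest plot for DTE, but no overall ITT hazard ratio for DTE.

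**Working it through.** **Text comparison**

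| Output for DTE (ITT, all subjects) | Protocol 10.3.5.1 | SAP |
|---|---|---|
| Superiority log-rank test | After non-inferiority (ordering in 10.3.5.2) | After non-inferiority (6.2.1.2) |
| Cox HR and 95% CI | No condition stated | Non-inferiority claimed and PH plausible (6.2.1.2) |
| PH assessment | No condition stated | Non-inferiority accepted (6.2.1.3) |

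The documents agree on the first row and differ on the other two.

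**Inputs for the size of the effect**

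- Margin 1.20, the rule for the upper limit and the approximation V ≈ events/4: SAP 6.2.1.1.
- Planning hazard ratio 0.7654 and 440 events: Protocol 10.4.
- On-treatment event count D: not in the documents. Assumed 440 (the ITT target), 300 and 200.
- The true hazard ratios below are taken to apply on treatment. The planning value is an ITT figure, so using it here is also an assumption.

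**The plan's own figures**

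HR = ln(1 − 0.264)/ln(1 − 0.330) = 0.7654, matching Protocol 10.4 ("Under the assumption of an exponential distribution, the hazard ratio equals 0.7654"). The Schoenfeld formula at two-sided 5%, 1:1 allocation and 80% power gives 440 events, and power at 440 events is 80.07%. Both agree with the protocol.

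**Chance that non-inferiority is not claimed**

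The SAP rule requires HR_est × exp(1.96/√V) < 1.2. With V = D/4,

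P(not claimed) = 1 − Φ( ln(1.2/HR) × √D/2 − 1.96 ).

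Example, HR = 1.0 and D = 440: ln 1.2 = 0.1823 and √440/2 = 10.488, with product 1.912. Then 1.912 − 1.96 = −0.048, Φ = 0.481, and P = 0.519.

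| True on-treatment HR | D = 440 | D = 300 | D = 200 |
|---|---|---|---|
| 0.7654 | 0.3% | 2.7% | 11.1% |
| 0.90 | 14.5% | 29.8% | 47.0% |
| 1.00 | 51.9% | 64.8% | 74.9% |
| 1.10 | 85.3% | 88.6% | 91.1% |

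At HR 0.90 and 440 events the rule gives 85.5% power (100 − 14.5), against the more than 90% stated in Protocol 10.4 for hazard ratios of 0.90 or below. That is a separate matter, but it explains why this row is higher than the protocol would suggest.

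**Observed value needed to pass**

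The largest passing estimate is 1.2 × exp(−1.96/√(D/4)): 0.995 at 440 events, 0.957 at 300 and 0.909 at 200. An estimate of exactly 1.0 passes only if D > (2 × 1.96/ln 1.2)² = 462.3. With 462 or fewer on-treatment events, any on-treatment estimate of 1.0 or above means the condition is not met.

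The realised count could differ from 440, because Protocol 5.3.3 projects the cut-off in advance and allows an earlier stop if the event rate is low.

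**The case against.** The strongest reply is that the SAP never says the hazard ratio is produced *only* if non-inferiority is met. It is based on protocol version 3.0 and its section 7 declares no departure from it, so the protocol's unconditional plan still stands and this is a mismatch of wording. Protocol 10.3.5.1 also leaves further detail to the SAP, and its hierarchy could be read as covering everything in that section. This has force: the percentages above are rates of non-inferiority failure, not of non-reporting. But a condition that removes a planned output is more than detail, and two readings of the primary estimate are a reason to reconcile the texts.

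Second, much other output survives:

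- SAP 6.2.1.1 calculates an on-treatment hazard ratio and upper limit whatever the result, and Protocol 10.3.5.2 plans a Cox hazard ratio with its interval in the non-inferiority section.
- SAP 6.5 plans component hazard ratios, and hazard ratios before and after new-onset atrial fibrillation, by analogy with 6.2.1.2.
- SAP 6.6.1 gives ITT subgroup hazard ratios.
- SAP 6.2.1.2 also says "Kaplan-Meier curves, one-sided log rank p-value, number of patients with event and incidence rate are provided", with no condition of its own, although the section opens with one. A rough rate ratio could be derived from those figures.

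All true, but none of these is the overall ITT Cox hazard ratio with its interval.

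Third, conditioning a hazard ratio on proportional hazards is not foreign to the protocol: section 10.3.7 does so for bleeding. For DTE, however, 10.3.5.1 states no such condition and considers time-dependent hazard ratios if non-proportionality is strong.

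Finally, no test, power figure or trial decision changes, and flowchart 1 of the SAP is not shown, so it could not be checked. Both points are correct.

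**Conclusion.** The concern holds. SAP 6.2.1.2 and 6.2.1.3 attach an on-treatment non-inferiority condition to three descriptive ITT outputs that Protocol 10.3.5.1 plans without it. The condition rarely matters if the design effect holds and most events occur on treatment. It usually matters if there is no effect or harm: failure in 52% to 75% of trials at a true hazard ratio of 1.0, and in 85% to 91% at 1.1. These ranges rest on the assumed on-treatment counts of 440 down to 200 and on V ≈ events/4. An overall ITT estimate reported after a failed test would follow the protocol but go beyond the SAP's stated rule, weakening its pre-specified status just when the result is neutral or unfavourable. The point should be fixed. Confidence is medium, because the hierarchy admits a wider reading and flowchart 1 was not available.

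**What to change.** In SAP 6.2.1.2 and 6.2.1.3, delete the non-inferiority condition on the hazard ratio, its interval and the proportional-hazards check. Keep it for the superiority test. Add a sentence such as: *The ITT Cox hazard ratio with two-sided 95% CI and the proportional-hazards assessment for DTE are reported descriptively whatever the test results.* If proportional hazards is doubtful, still report the Cox hazard ratio, as Protocol 10.3.5.1 plans, with time-dependent hazard ratios alongside. Check that flowchart 1 agrees.

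The cost is SAP wording only. The SAS code is already in both sections, and alpha, sample size and data collection are unaffected.
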